3.0	24 Jun 2014	[name]	First circulated version, and with ethics approval. No patients enrolled under this version at St. Michael's Hospital.
4.0	08 Feb 2016	[name]	Reformat without changes to protocol; circulated for comments.
4.A	08 Feb 2016	[name]	Modify wording, no material changes to protocol
4B	09 Feb 2016	[name]	Further modify wording, no material changes to protocol
4C	09 Feb 2016	[name]	Alter methodology to promote study objectives more efficiently
4D	09 Feb 2016	[name]	Incorporate comments and suggestions.
5.0	28 Mar 2016	[name]	Revised circulated version. This is the first version to be implemented at the St. Michael's Hospital site. Changes from version 3.0 are: 
 (a) Formatted to resemble ICH and FDA templates (b) One replacement application of DermGEN is permitted, if warranted. (c) Now provides for experience with up to 3 patients excluded from the study analysis, before finalizing procedures. (d) Now specifically allows inclusion of patients with DFU healing after treatment of underlying osteomyelitis. (e) Allows for vacuum-assisted closure device over the wound. (f) Utilizes the SF-12 questionnaire in place of the SF-36, and LUMT document in place of MDLUC-AQ.

SPONSOR APPROVAL PAGE

**A Pilot Safety and Efficacy Study of DermGEN Dermal Regeneration Scaffold
for the Treatment of Diabetic Foot Ulcers**

Version: 5.0

Date: 28 March 2016

Approved for DeCell Technologies, Inc. by:

[name], PhD

Date:

INVESTIGATOR PROTOCOL AGREEMENT PAGE

A Pilot Safety and Efficacy Study of DermGEN Dermal Regeneration Scaffold for the Treatment of Diabetic Foot Ulcers

I agree, as an Investigator conducting this study:

- To assume responsibility for the proper conduct of the study at this site.
- To conduct the study in compliance with this protocol, with any future amendments, and with any other written study conduct procedures provided and reviewed and approved by DeCell Technologies, Inc. (“DeCell”)
- Not to implement any significant deviations from or changes to the protocol without agreement from the sponsor and prior review and the written approval from the Institutional Review Board, except where necessary to eliminate an immediate hazard to the patients, or for administrative aspects of the study (where permitted by all applicable regulatory requirements).

1. STUDY BACKGROUND

1.1 Study Rationale

The number of people afflicted by diabetes is increasing significantly every year worldwide, with an estimated 366 million affected in 2011 that is projected to reach 439 million by 2030 — approximately 10% of the world's adult population. Of that population, up to 25% are expected to have chronic foot ulcers which can lead to significant complications: 85% of lower extremity amputations are an end result of diabetic ulcers². This equates to a limb being amputated somewhere in the world every 20 seconds due to diabetes^{3,4}. In Canada, 9 million people are diabetic and between 1.35 and 2.25 million will suffer from chronic foot ulcers⁵. In Nova Scotia, which has one of the highest rates of diabetes in Canada, more than 98,000 people are affected by diabetes, with between 14,700 and 24,500 people afflicted with chronic foot ulcers^{6,7}. In addition, the problem of diabetes-related ulcers in Nova Scotia is projected to grow, with the number of people with diabetes increasing by at least 3% by 2020.

The most common form and first line of treatment for chronic diabetic foot ulcers is the use of weekly debridement. Patients are assessed initially to determine which detriments to healing (infection, vascular insufficiency, uncontrolled diabetes, smoking, poor nutrition, deformity and poor offloading) of an ulcer may be present. These detriments are then treated for optimization over the ensuing weeks to months. During this time, patients will have local wound care with debridement and the wound will be cleaned of any infected and necrotic tissue, using sharp debridement until a pristine bleeding wound is obtained. The wound site is then wrapped with a non-adherent and moist dressing followed by dry gauze, and the site is protected from weight-bearing (i.e., is off-loaded). This procedure is repeated at set intervals until the wound either heals, or (once all detriments to healing have been optimized and the wound has not healed) treatment is determined to be futile. The success rate for complete wound closure with standard care is very low and variable, with a range from single digit percentage to as high as 50%, and if healing does occur, it takes on average 8 to 9.5 weeks^{8,9}. However, previous studies have shown that reduction in the area of the chronic wound during the first four weeks of treatment is a predictor of complete healing at 12 weeks¹⁰. Diabetic foot ulcers that persist more than 4 weeks have 5-fold higher risk of infection¹¹. Development of an infection in a foot ulcer increases the risk for hospitalization 55.7 times and the risk for amputation 155 times¹¹. Any wound that remains unhealed after 4 weeks is cause for concern, as it is associated with worse outcomes, including amputations¹².

Costs associated with treating diabetic foot ulcers range by country and region, but in all cases are a major economic burden. For example, in the U.S. in 2007, \$116 billion was directly spent on diabetes, with at least 33% of these costs linked to the treatment of diabetic foot ulcers with an average cost per ulcer episode of \$13,179. In Canada, the average cost of treating a diabetic foot ulcer is \$10,736, with more than \$150 million in total spent annually⁵.

Although standard of care is the most widely used treatment for diabetic foot ulcers and the main form of treatment in Canada, there are a number of advanced wound care products available to the clinician. Most products fall under the category of a biologic dressing ranging from cell-containing living skin analogs such as Apligraf® (Organogenesis) and Dermagraft® (Shire) to tissue-derived decellularized scaffolds like GraftJacket® decellularized human dermis (Wright Medical), Oasis® porcine small intestinal submucosa (Smith and Nephew), and EpiFix® dehydrated human amnionic membrane (MiMedix). These products are designed and promoted as wound healing and tissue regeneration matrices that, once applied to the patient, are integrated with and then resorbed by the patient's body. The use of these treatments, however, has been limited due to their prohibitive cost and inconsistent clinical performance. For example, market leaders Apligraf®, Dermagraft®, and Graftjacket® range in price from \$1,500-\$2,500 USD for a 2" x 2" graft.

Most importantly, although initial limited clinical studies used to prove effectiveness for marketing and reimbursement purposes were successful, performance of these products in general use has proven to be far less successful. The most expensive (and cell-based) products, Apligraf® and Dermagraft® are in fact not incorporated after application, and eventually are sloughed off the wound due to death of the cellular material within the graft. Further, even when successful, they have required from 6 to 10 reapplications of the product in order to achieve a wound closure rate of 35-55%¹⁴. In the case of Dermagraft®, costs of manufacture, poor sales, and a recent failed clinical trial for venous ulcers prompted Shire to sell Dermagraft® assets to Organogenesis with a loss of \$650 million USD¹⁵. In the case of the ultimate market leader in terms of sales, GraftJacket® decellularized human dermis (Wright Medical), inconsistent and low rates of healing have been attributed to the failure to adequately remove donor cell materials (DNA/RNA, HLA cell membrane proteins) while preserving the natural architecture of the remaining extracellular matrix (ECM) scaffold^{16,17}. The presence of cell remnants and disruption of tissue architecture increases inflammatory reactions both in-vitro and in-vivo, leading to inadequate and incomplete healing^{18,19}. It should be noted that only Dermagraft® has been approved for use in Canada, and treatment of most diabetic foot ulcer patients in Canada consists of debridement alone.

In order to address this unmet need for a safe, consistent, and effective treatment for diabetic foot ulcers, a new start-up company located in Halifax, DeCell Technologies Inc. (“DeCell”), has developed its product DermGEN, a sterile, highly-purified, decellularized regeneration scaffold derived from donated human skin. This product and company have spun out of research conducted by [name] (School of Biomedical Engineering, Dept. of Surgery) at Dalhousie University. [name] patent pending decellularization technology has been shown to be superior to others in achieving very high levels of cellular material removal (95-99%) including DNA/RNA, HLADR, HLA-ABC, and cytoskeletal proteins beta-actin and vimentin²⁰. In addition, the process maintains the natural composition and architecture of the ECM while creating a validated sterile product (See Appendix 1, Figures 1-5, Table 1). Using an immune-competent rat biocompatibility model (ASTM standard F1408 -97) and directly comparing DermGEN to the leading competitor Graftjacket®, there was consistent superiority as DermGEN demonstrated lower inflammation, more-rapid vascularization, and better tissue remodeling at 1, 3 and 9 weeks post-surgery (See Appendix 1, Figures 6-14). It should be noted that a more rigorous model was used here with excellent results, as human tissue was implanted into a rat (that is, a xenograft). In practice, the human decellularized dermis will be used to treat human patients and therefore would be a much better situation with transplantation within the same species (i.e., an allograft). DeCell Technologies Inc. has already received approval from Health Canada to use DermGEN in humans (See Appendix 2).

The purpose of this clinical trail is to perform a limited pilot study, the first study in man to assess the effectiveness and safety of DermGEN in the treatment of non-healing diabetic foot ulcers (DFU), as a preliminary to studies in larger populations and different wound types. This will be a one-arm prospective study with control comparisons made to historical data for standard of care treatment of DFU’s (debridement, sterile moist bandages, off-loading of the foot) obtained within the Multi-Disciplinary Leg Ulcer Clinic (MDLUC) at the QEII Hospital. This study in Halifax will be mirrored in one other participating health care center in Toronto, with each center enrolling 5-10 patients for a total of 20 patients. Funding for this trial will be from a recently awarded (January 2014) CIHR Proof of Principle (POP) II Grant with [name] (Orthopaedic Surgeon, QEII Hospital) as Principal Investigator and [name] (Associate Professor, Biomedical Engineering and CEO of DeCell Technologies Inc.) as the industrial sponsor.

Since previous studies have shown that reduction in the area of the chronic wound during the first four weeks of treatment is a predictor of complete healing at 12 weeks¹⁰ and that DFU’s persisting more than 4 weeks have 5-fold higher risk of infection¹¹, we will be determining and comparing the reduction of wound size for our study at 1 and 4 weeks. Our primary outcome measures will be the proportion of patients with

complete healing at 12 and 20 weeks. Time to complete healing, incidence of recurrence of ulcer, incidence of adverse events, wound characterization, and mean and median wound size will also be documented and compared over the 20-week scope of the study.

Given the current standard of care for diabetic foot ulcers, DermGEN may be transformative to a new standard of care that will have a great impact on the lives and wellness of diabetic Canadians. The dramatic statistic of a limb being amputated somewhere in the world every 20 seconds due to diabetes is simply unacceptable. Having a cost-effective product like DermGEN available to clinicians could truly alter this appalling outcome.

1.2 Pre-clinical in vitro Data

See Investigators' Brochure.

1.3 Pre-Clinical in vivo Data

See Investigators' Brochure.

1.4 Safety Considerations

DermGEN is expected to be a safe wound covering, with a favourable risk-benefit ratio as outlined below.

1.4.1 Harms

Possible complications with the use of DermGEN include maceration, specific or non-specific immune response, graft infection, graft resorption, or graft non-integration. Given the nature of the treatment and location and type of wound being treated, most adverse events may be stopped through the cessation of treatment with DermGEN.

1.4.2 Benefits

The possible benefits of the proposed study include a faster, more effective, and more cost effective resolution of a chronic diabetic foot ulcer.

1.4.3 Financial Compensation

Patients enrolling in this study receive no financial reward for participation. The study treatment is provided at no cost.

2. STUDY OBJECTIVES

The purpose of this clinical trial is to perform a limited pilot study to indicate the safety and effectiveness of DermGEN in the treatment of non-healing diabetic foot ulcers (DFU).

Adverse events incidence is the only objective regarded as a safety issue.

2.1 Primary Objectives

Primary Outcome Measures:

1. Mean and median reduction in wound area in the first 4 weeks.
2. Proportion with complete healing in the first 12 weeks. (*Complete healing is defined as 100% epithelialization without drainage.*)
3. Incidence of adverse events.
4. Impact of treatment, as measured by LUMT (Leg Ulcer Measurement Tool) and SF12 (See Investigational Plan, below)

2.2 Secondary Objectives

Secondary Outcome Measures:

1. Proportion with complete healing at any time point
2. Time to first-measured complete healing
3. Incidence of recurrence after complete healing
4. Change in wound characteristics
5. Mean and median reduction in wound area at 12 weeks

3. INVESTIGATIONAL PLAN

3.1 Study Design

This is an interventional, single-arm, prospective study of DermGEN applied to diabetic foot ulcers.

The study treatment will be conducted for a total of up to 20 weeks, and 15-20 patients will be enrolled.

In order for the treatment team to gain experience with the sizing and application of DermGEN and the most suitable off-loading methodology, the first one to three patients may have differing closure procedures, and will not be included in the per-protocol analysis of the study (although all safety data will be reported). Thereafter, the team will specify a single regimen of procedures, dressing types, and off-loading methodology to be used for all subsequent patients.

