3.1.2 Clinic Admission (Day 0)

After enrollment and an initial assessment (time zero data), patients will be treated with DermGEN decellularized human dermal matrix. Following standard of care procedures, the wound will be debrided to provide healthy tissue margins and a bleeding wound bed. A 4 cm x 4 cm piece of DermGEN will be prepared by sizing to approximately 2-3 mm past the margins of the ulcer with the dermal side in contact with the wound bed, and securing it to the wound with sutures.

A non-adherent dressing will be used to cover the DermGEN graft, followed by a moisture retentive dressing and either (a) a compressive dressing; or (b) a vacuum-assisted wound closure dressing (“VAC-Assist”). All patients will have the same brands and types of dressings applied, except for the first 1 to 3 patients treated (see final paragraph, section 3.1 above).

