3.1.3 Subsequent Clinic Visits (Weeks 1, 2, 3, 4, 12, and 20)

Follow up visits will be at 1, 2, 3, 4, and 12 and 20 weeks and as required for clinical care of active detriments to healing and local wound care.

The LUMT will be administered at each of the 1, 2, 3, 4, and 12 and 20 weeks FU visits in order to capture data relevant to the study. The SF-12 survey will be administered at time 0, 4, 12 and 20 weeks post-treatment.

Digital photography will be utilized to capture the appearance and size of the ulcer at each visit. Clinic photographs will be taken with the digital camera supplied by DeCell. Other photographs to demonstrate the condition of the wound between clinic visits may be taken with any digital camera (including smartphones), and a measuring ruler must be visible in each picture. Patients and caregivers are to be encouraged to take their own photographs if the wound ever becomes uncovered or visibly stained – again ensuring that some ruler appears in the photos – and copies should be provided to the study staff.

Dressing changes will occur at each visit, and a record of these changes kept. All patients will receive appropriate wound off-loading using a device appropriate to ulcer location. All post-treatment complications will be recorded on the appropriate case report form.

Patients with complications that may be managed by further treatment, for example antibiotic administration or reapplication of another DermGEN graft, will remain in the study.

For any subject who requests study withdrawal or is withdrawn by the investigator, the reason for study discontinuance will be recorded by the Principal Investigator on the appropriate case report form.

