4.3 Exclusion Criteria

A subject will not be considered eligible to participate in this study if any one of the following exclusion criteria is satisfied:

1. Evidence of gangrene on affected foot.

2. Ulcer is over Charcot deformity (fractures or dislocation).
3. Ulcer is non-diabetic in etiology.
4. Ulcer has tunnels or sinus tracts that cannot be completely debrided.
5. Medical condition(s) that in the Investigator's opinion make the patient inappropriate for study
6. Patient has/had malignant disease not in remission for 5 years or more
7. Patient has acute or chronic hepatitis, cirrhosis, serum albumin <2.0 gm/dL, or has alkaline phosphatase or LDH at twice the normal upper limit
8. Patient receiving oral or parenteral corticosteroids, immunosuppression or cytotoxic agents, or is anticipated to require such agents during study
9. Patient received radiation therapy within 30 days of Day 0 of study
10. Patient has AIDS or is infected with HIV
11. Patient has participated in another study using investigational drug(s) or device within the previous 30 days
12. Obvious clinical signs and symptoms of ongoing cellulitis or osteomyelitis
13. Patient has any other condition which seriously compromises their ability to complete the study
14. Patient has known allergies to antibiotics, such as penicillin and streptomycin
15. Patient has a history of bleeding disorder
16. Patient received elective osseous procedures to the study foot within 30 days prior to screening visit, *except* that patients whose DFU overlies an area of treated osteomyelitis may be included, providing there exists a suitable base for application of the DermGEN.

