6.1.2 Enrollment (Day 0)

After enrollment and an initial assessment including the Leg Ulcer Measurement Tool [LUMT] (see Appendix 4), patients will be treated with DermGEN decellularized human dermal matrix. Following standard of care procedures, the wound will be debrided to provide healthy tissue margins and a bleeding wound bed. A 4 cm x 4 cm piece of DermGEN will be prepared by sizing to approximately 2-3 mm past the margins of the ulcer and securing to the wound with sutures ensuring that the dermal side is in contact with the wound bed. [*The dermal side of DermGEN can be identified by the following: (i) apply a drop of blood or contact with blood from the wound bed to one surface of the graft; (ii) rinse blood off with sterile saline; (iii) if blood does not wash off entirely, this is the dermal side—the epidermal side will not retain visible quantities of blood.*] A non-adherent dressing will be used to cover the DermGEN graft, followed by (a) a moisture retentive dressing and a compressive dressing, or (b) dressings as specified for use by all patients, once the first 1 to 3 patients have been treated (see section 3.1, above). Suitable off-loading will also be provided, with careful instructions for use.

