6.1.3 Follow-up Procedures (Week 1 to Week 20)

Follow up visits will be at Weeks 1, 2, 3, 4, and 12 and 20, and as required for clinical care of active detriments to healing and local wound care. The Leg Ulcer Measurement Tool [LUMT] will be completed at each of the Weeks 1, 2, 3, 4, 12, & 20 follow-up visits in order to capture data relevant to the study. In addition, digital photography will be utilized to capture the appearance and size of the ulcer at each visit. The SF-12 survey will be administered at Day 0, and at the Weeks 4, 12 and 20 visits.

Dressing management will follow and a record of all changes will be kept. All patients will receive wound off-loading using a device appropriate to ulcer location.

All post-treatment complications will be recorded on the appropriate case report form. Patients with complications that may be managed by further treatment, for example antibiotic administration or application of one replacement DermGEN graft, will remain in the study.

For any subject who requests study withdrawal or is withdrawn by the investigator, the reason for study discontinuance will be recorded by the Principal Investigator on the appropriate case report form. Stopping treatment or withdrawal from the study will occur when:

- (i) patient is non-compliant with home care regime (e.g. not wearing off-loading cast),
- (ii) presence of recurrent, untreatable infection,
- (iii) patient develops illness after enrollment that may unduly affect ulcer healing,
- (iv) patient requires more than one re-treatment with DermGEN

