7. DATA ANALYSIS AND STATISTICAL CONSIDERATIONS

7.1 Statistical and Analytical Plans

7.1.1 Analysis Populations

Safety population: all subjects will be included in the analysis for safety.

Efficacy population: all subjects excepting the first 1 to 3 (i.e. those treated before standardization of procedures) will be included in the analysis to seek efficacy signals.

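### Does requiring one off-loading methodology after the lead-in conflict with choosing the device by ulcer location, and does that undermine the efficacy set?

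*Protocol*

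**What the plan says.** Section 3.1 gives the purpose of the lead-in: "to gain experience with the sizing and application of DermGEN and the most suitable off-loading methodology". Closure procedures may differ in those patients, and they are left out of the per-protocol analysis although their safety data are reported. Then: "Thereafter, the team will specify a single regimen of procedures, dressing types, and off-loading methodology to be used for all subsequent patients".

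Section 7.1.1 builds the efficacy population on this: "all subjects excepting the first 1 to 3 (i.e. those treated before standardization of procedures".

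Off-loading also appears in three procedural sections:

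- Section 3.1.3: "All patients will receive appropriate wound off-loading using a device appropriate to ulcer location".
- Section 6.1.3: "All patients will receive wound off-loading using a device appropriate to ulcer location".
- Section 6.1.2: "Suitable off-loading will also be provided, with careful instructions for use".

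None of these sentences names the single regimen or makes an exception for the lead-in. For dressings the protocol does make the link. Section 3.1.2 says "All patients will have the same brands and types of dressings applied, except for the first 1 to 3 patients treated" and points back to section 3.1, and section 6.1.2 does likewise.

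**The concern.** Read quickly, one off-loading methodology for all later patients and a device that varies with ulcer location are incompatible. The only entry criterion that touches location is the exclusion "Ulcer is over Charcot deformity (fractures or dislocation", so ulcers at different sites on the foot, and hence more than one device, are to be expected.

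That seems to leave two unattractive readings. If the methodology is the same for everyone in every detail, a later patient with another device has not had the regimen on which section 7.1.1 relies. If it is only a rule to match device to location, the rule already applies from the first patient, and the lead-in appears to settle nothing about off-loading.

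Section 1.1 names poor off-loading as an obstacle to healing. The 4-week reduction in wound area and the 12-week healing proportion are primary outcomes, and section 7.1.3.2 expects the conclusions to inform later studies. A reader would want to know whether the figures describe one off-loading approach or several. In addition, no section requires a dated record of when the regimen was fixed, so the number excluded (one, two or three) might seem open to choice after the event.

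**Working it through.** The plan gives no figure to reproduce. Section 7.2 bases the sample size on precedent without a power calculation, and section 7.1.2 limits the analysis to descriptive statistics. The check is a comparison of the texts, followed by arithmetic on what could change.

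**1. Can all the sections hold together?** Section 3.1 fixes a methodology; sections 3.1.3 and 6.1.3 fix a property of the device. The latter state a general requirement and do not say which device belongs to which site or how it is to be used. The lead-in can settle that scheme, after which it is used for everyone, while the general requirement binds from the first patient. On this reading sections 3.1, 3.1.3, 6.1.2 and 6.1.3 are all satisfied and the lead-in still has something to decide about off-loading. The choice between two readings is therefore not exhaustive. In section 6.1.2 the off-loading sentence also directly follows the cross-reference to section 3.1.

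**2. Does the efficacy set depend on it?** Section 7.1.1 excludes by order of treatment. With 15 to 20 enrolled (section 3.1) and 1 to 3 excluded:

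- 15 enrolled: 15 − 3 = 12 to 15 − 1 = 14.
- 20 enrolled: 20 − 3 = 17 to 20 − 1 = 19.

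No device term enters these counts. Reconciling the off-loading text in either direction moves no patient in or out.

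**3. How much could mixed devices matter?** The documents give no healing rate by device, so every input here is assumed: a 10 to 20 point difference in healing between two devices, and 25% to 50% of efficacy patients on the second.

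- Shift = share × difference: 0.25 × 10 = 2.5 points up to 0.50 × 20 = 10 points.
- The same difference confined to the lead-in patients, had they been kept: 1/20 × 10 = 0.5 points up to 3/15 × 20 = 4 points.

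The first range exceeds the second only because the same assumed difference is multiplied by 25–50% in one case and by 5–20% in the other. It also credits the lead-in patients with a device difference alone, although section 3.1 sets them apart for sizing, application and closure as well.

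**4. How much could an undated count matter?** As an upper bound, suppose the number excluded (k = 1, 2 or 3) were picked with full knowledge of outcomes to give the best result.

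- Healing rate: E[max over k of healed/(N − k)] − p, by exact enumeration for assumed p of 10% to 50%. The gain is 1.27 to 2.95 points at N = 15 and 0.92 to 2.14 points at N = 20.
- Mean 4-week area reduction, independent normal outcomes, by simulation: about 0.053 SD at N = 15 and 0.038 SD at N = 20. For an assumed SD of 30 to 50 points that is about 1.6 to 2.6 and 1.1 to 1.9 points.

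**5. Sampling error for comparison.**

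- 6 healed of 12: exact (Clopper-Pearson) 95% interval 21.1% to 78.9%.
- Mean area reduction at n = 12: 1.96 × SD/√12 = 17.0 points (SD 30) or 28.3 points (SD 50).

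Every effect in steps 3 and 4 is smaller than the corresponding margin.

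**The case for a change.** The best case for a change is that the reading which harmonizes the sections is nowhere written down. For dressings the protocol states the lead-in exception and refers back to section 3.1; for off-loading it does neither. One site could vary the device by patient under sections 3.1.3 and 6.1.3, while another could think section 3.1 forbids it. Failure to wear the off-loading cast is a ground for withdrawal (sections 4.6.2 and 6.1.3), so off-loading also bears on who stays in follow-up. The repair would cost a sentence or two and a dated record.

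Part of this stands. No section says whether the device may vary within the single methodology, and a reader of the results would be helped by knowing. It is also true that the count of one to three is left open and that no dated record is demanded.

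The rest does not carry. The withdrawal ground concerns adherence to the home-care regime, whichever device was supplied, and section 7.1.1 keeps every subject after the lead-in in the efficacy set. Section 3.1 works forward in time: the regimen is specified and then used for those who follow, and nothing provides for choosing the count after outcomes are known. Section 3.1 already lists the components to be standardized. Dressing changes are recorded (sections 3.1.3 and 6.1.3), source documents must support the case report forms (section 8.1), and important deviations in conduct or subject management are to be described (section 7.1.3.3). The changeover is therefore likely to be traceable.

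**Conclusion.** The concern identifies an ambiguity of wording and does not establish a contradiction. Its reach is limited to how uniform off-loading is within the efficacy set. It alters neither the membership of that set (12 to 19 patients across the planned enrolment) nor any figure stated in the protocol, and no hypothesis test depends on it.

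The possible shifts are 2.5 to 10 points on the healing rate from mixed devices, and at most about 3 points from a count chosen with full hindsight. The first rests on assumed device differences that the documents do not support. The second rests on a selection that the text does not provide for. Both are small beside the sampling error of a first-in-human pilot of this size.

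Followed as written, the plan still yields a sound descriptive result. Those reporting it can describe the off-loading actually used and say when the regimen was settled. How the off-loading sentences are best aligned is a clinical matter for the sponsor and investigators and is not judged here. A linking sentence would tidy the text, but the analysis does not need it.
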